**Abbreviations and Definitions:**

AE	Adverse Event/Adverse Experience
CI	Confidence Interval (confidence limits)
ETtau	Efficacy Trial for the Treatment of Acute Urticaria
ED	Emergency Department
MedDRA ©	Medical Dictionary for Regulatory Activities
N	Number (typically refers to subjects)
NI	Non-inferiority
SAP	Statistical Analysis Plan
SAE	Serious Adverse Event
SD	Standard Deviation
WHO	World Health Organization

---

**1. PREFACE**

This document describes in detail the statistical methods that will be used to summarize and analyze the background, safety, and efficacy data from protocol ETtau-03 entitled “*A Phase III, multi-center, double blind, randomized, active controlled clinical trial to evaluate the non-inferiority comparing Cetirizine injection 10 mg, to Diphenhydramine injection 50 mg, for the treatment of acute urticaria.*” (dated April 10, 2017).

**2. STUDY OBJECTIVES AND ENDPOINTS**

This will be a multicenter, parallel group, randomized, double-blind, active controlled, Phase III clinical study of cetirizine injection, 10 mg/mL, compared to diphenhydramine injection, 50 mg/mL (Benadryl or generic equivalent), in approximately 254 subjects with acute urticaria requiring treatment in Emergency Departments (ED), hospitals, Urgent Care Centers, or Allergy Clinics.

The objectives of this study are:

The primary objective of this study is to establish the non-inferiority of Cetirizine injection with respect to Diphenhydramine injection in reducing patient reported pruritus severity score at 2 hours after treatment of acute urticaria. The secondary objectives are as follows:

1. Record the percentage of subjects who return to treatment center after discharge (i.e. 2nd visit within 24 hours after discharge)
2. Record and compare sedation scores between treatments
3. Record and compare time-to-discharge between treatments
4. Record and compare changes in patient reported pruritus severity score at 1 hr post treatment and at time of discharge.
5. Record and compare extent of urticaria/erythema scores, and their changes from baseline at various time points after treatment.
6. Document the percentage of subjects experiencing adverse events (AEs) or serious adverse events (SAEs) from the both study drugs.
7. Document the percentage of subjects requiring rescue medication prior to discharge, e.g. epinephrine, bronchodilators, steroids, etc.,
8. Record symptom recurrence rate and additional symptoms occurrence within 24-48 hours after subject discharge from treatment centers.
9. Record the need for medication after discharge.

The primary demonstration of efficacy will be non-inferiority of cetirizine to diphenhydramine with regards to the change from baseline in patient rated pruritus severity at 2 hours post-treatment.

The following outcomes that will provide key support to the primary efficacy claim:

- 
- *Return to Treatment Center:* During the 24 and 48 hr follow up questions, subjects will be asked if they had to return to a treatment facility for their urticaria. Subjects will be flagged as either YES or NO.
  - *Time Spent at Treatment Center:* This will be defined as the difference between the time of treatment administration and of Readiness for Discharge. If a patient is admitted to hospital (not to go home), or stayed in ED observation overnight, the time to “Readiness for Discharge” is not recorded. These subjects will not be included in the summary analyses.

In addition, the following outcomes will be assessed by treatment as supportive information for the application:

- 1) *Pruritus Treatment Success:* A subject will be defined as having treatment success if the patient rated pruritus severity score at 2 hrs is at least 1 unit less than at baseline.
- 2) *Patient Rated Pruritus Severity Scores change at other time points:* The scores change/reduction from baseline at other assessment times (i.e.: 1 hr and at discharge)
- 3) *Sedation Score:* Subjects will be asked to rate their sedation at baseline, 1 hr, 2 hr and discharge.
- 4) *Physician Rated Extent of Urticaria/Erythema Scores:* Physicians will rate the percentage of body area affected and the intensity of redness on scales from 0 (none) to 3(severe) at baseline, 1 hr, 2 hr and discharge. The average of body area and intensity scores at each assessment time will be the Extent of Urticaria/Erythema score for that assessment time. This outcome will have the range from 0 to 3 with increments of 0.5 units.
- 5) *Proportion of Subjects Needing Rescue Medication:* A subject will be defined as needing rescue, if at any time after study drug and prior to readiness for discharge, the subject requires other medications for the symptoms of urticaria.
- 6) *Effectively Treated:* The investigator’s judgment of a subject’s effective treatment of symptoms (Yes/No).
- 7) *Symptom Recurrence:* Subjects will be followed up after 24 and 48 hours after discharge and asked if they have had any recurrence of symptoms since discharge.
- 8) *Need for Prescription Medications:* During the 24 and 48 hr follow up questions, subjects will be asked if they took any medications prescribed at discharge since discharge.
- 9) *Need for Additional Medications:* During the 24 and 48 hr follow up questions, subjects will be asked if they took any additional medications since discharge.
- 10) *Return to Normal Activity:* During the 24 and 48 hr follow up questions, subjects will be asked if they had returned to their normal activities.

See [Section 10.4](#) for detail on the specific analyses to be performed for each outcome.

---

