Just before the study medication is administered, the study investigator or designee will record the following baseline data: vital signs, the extent of urticaria and erythema, the severity of pruritus by patient, and the level of sedation by patient. See [Attachment B](#) for detailed description of symptom assessment. The same measures will be assessed again at 1 hour and/or 2 hours after the injection, and/or at the Time of "Readiness for Discharge" which can happen at any time after the 1-hour assessment if the symptom score has reached zero at 1hr. If symptom score is not zero prior to 2 hr, patient must be kept at the treatment center for at least 2 hours. At these same time intervals, participating patients will be asked to self-rate (recorded by study staff) the severity of their pruritus and their level of sedation. The patient's responses will be recorded by the investigator/designee on the designated Source Document or eCRF as "patient assessment scores". The time that the investigator/designee determines that patient is physically and mentally fit to be discharged from the center (Time of "Readiness for Discharge"), , will be recorded in the source documents. If the Time of "readiness for discharge" happens longer than 20 minutes from the previous assessment, then the "readiness for discharge assessment" should be done. If the Time of "readiness for discharge" happens within 20 minutes of the previous assessment and the symptom score does not change from the previous assessment, then the "readiness for discharge" assessment is not needed, because the previous assessment can be treated as the "readiness for discharge assessment".

Site staff should ensure that the patient has appropriate transportation to their destination; under no circumstances should a study participant be permitted to drive themselves if the sedation score is at "1" or higher. The time that the patient actually leaves the treatment center is also recorded.

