Before discharge, patients will be instructed that a member of the site staff will telephone them at approximately the same time or the next convenient time (e.g.: if patient is discharged at 3 am, the site staff will telephone the patient at ~8 am) the following day, and the day after (i.e. ~24 hours, and ~48 hours later) to ask them a few short questions to follow up on the treatment of their acute urticaria (See [attachment C](#)). Patients will be asked to provide contact telephone number where they can be reached and also given a telephone number for them to call in the event that they are not contacted. Patients will also be instructed to call this number to report any AEs or SAEs they may have experienced.

The decision to discharge the patient (Time of "Readiness for Discharge") can be taken by the Investigator/designee provided the following criteria are met:

- 1) Symptoms of the acute allergic reaction have been effectively treated based on investigator/designee's opinion (*Note: if rescue drugs are used, patients are deemed not effectively treated by the study drug, but effectively treated by rescue drugs.*)
- 2) Patient is alert enough (sedation scores = 0) to understand Discharge Instructions
- 3) Based on the investigator's judgment, the patient is fit to be discharged

Note:

- i) *If patient is fit to be discharged, but not alert enough to drive home when the sedation score is at "1" or higher, he/she may be kept for a maximum of 5 hours (to make it practical for research personnel). But appropriate arrangement must be done, such as: call for a taxi, arrange a friend or relative to help drive, or ask patient to stay in the waiting room until sedation goes away, etc.*
- ii) *Standard discharge instruction should be given. If medications are prescribed at discharge, instruct patients take them "as needed"*
- iii) *In the event if the symptoms were not effectively treated, patients will be treated following the standard of care by attending physician.*
- iv) *If "Time of Readiness for Discharge" happens prior to the 2 hour assessment, the "patient Pruritus Score" must be Zero, otherwise the patient has to be kept in the treatment center for at least 2 hours.*

All AEs and SAEs that are reported after the patient signs an ICF will be recorded in the source documents and/or captured in the CRF.

Study procedures and their timing are summarized in the Study Schedule, Protocol [Attachment A](#).

5. Study Population

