6.4.5 Concomitant Medications/Rescue Drugs

To ensure optimal patient management, additional medications, e.g. epinephrine, steroids, or etc., may be given during the study if deemed necessary by the investigator/designee. However, if without medical complication, all effort should be made to have the patient complete at least the 1 hour assessments prior to administration of the rescue medication. If rescue medication is needed very shortly after study drug administration (e.g. within ~10 -15min), this indicates that the patient might have anaphylaxis. This patient should be withdrawn from the study, because he/she should have been excluded during screening.

The product label of the rescue drugs should be followed to determine the appropriate dose.

The identity, dose, frequency and route of administration of all medications being taken prior to study enrolment will be recorded, as well as all concomitant medications administered during the study (rescue drug).

6.5 *Clinical and Safety Evaluations*

Study procedures and their timing are summarized in the Study Schedule, Protocol [Attachment A](#). All subjects who received at least one dose of study medication will be included in all analyses and safety analyses.

7. Clinical/Efficacy Outcome and Measures

7.1 *Primary Clinical Efficacy Measure*

The primary clinical efficacy outcome measure is the 2-hour patient rated Pruritus Severity Score Reduction/Change from Baseline (**D2**) as defined under [Attachment B](#), comparing between the two treatment groups.

7.2 *Key Secondary Clinical/Efficacy Measures*

The following key secondary clinical or efficacy measures will be assessed for each patient:

- 1) The need to return to treatment center after study discharge (i.e. 2nd visit within approximately ~24 hours after discharge)
- 2) Time spent at the treating center (time from treatment administration to Readiness for discharge)

7.3 *Other Clinical/Efficacy Measures*

The following other clinical or efficacy measures will be assessed for each patient:

- 1) Pruritus treatment success (% of patients), defined as a patient who had the Pruritus Severity Score Reduction of at least 1 unit for the 2-hour patient rated Pruritus Severity score from Baseline (**D2**) as defined under [Attachment B](#), comparing between the two treatment groups.
- 2) Patient rated pruritus severity scores reduction/change from baseline (D1 & D3) at 1 hour and at "time of discharge"

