**9.11. Changes from Protocol Planned Analysis**

The protocol included collecting information on the reason for use of rescue drugs (secondary objective #7), however, it was determined at the time of CRF development that capturing such data would not add to the determination that a rescue medication was given. Therefore, this was not captured.

The sample size justification in the protocol was not updated to match the final methodology used. While both the protocol and the SAP sample size justifications results in the need for 127 subjects per treatment arm, the assumptions in this SAP are more indicative of the actual assumptions and methodology used to arrive at this sample size.

The protocol did not make provisions for subjects who needed to be hospitalized or kept in the ED overnight for observations. The SAP covers the needs to treat the time spent at the treatment center to “missing” for these subjects.

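### Time spent at the treatment center, a key secondary, has no value for patients admitted or kept overnight; in the visible text they drop out of the comparison and are not counted by arm

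*SAP*

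**What the plan says.** SAP 2 measures the endpoint from treatment administration to readiness for discharge. For patients admitted to hospital or kept in ED observation overnight no readiness time is recorded, and "These subjects will not be included in the summary analyses".

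SAP 9.11 gives the reason: "The protocol did not make provisions for subjects who needed to be hospitalized or kept in the ED overnight for observations". It continues: "The SAP covers the needs to treat the time spent at the treatment center to" missing for them. SAP 10.2 also sets the time to missing for patients who turn out not to have the disease.

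Other parts of the plan bear on this:

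- Protocol 7.2 introduces its two key secondaries with "The following key secondary clinical or efficacy measures will be assessed for each patient".
- Protocol 10.2.7 plans inferential comparisons of both, adjusted for multiplicity. SAP 9.3 names them as key support for the efficacy claim and applies Holm-Bonferroni.
- SAP 7 places all efficacy analyses on the ITT population.
- Protocol 4 makes readiness depend on three things: "Symptoms of the acute allergic reaction have been effectively treated based on" the investigator's opinion; "Patient is alert enough (sedation scores = 0) to understand Discharge Instructions"; and the investigator's judgment that the patient is fit to leave.

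**The concern.** Whether a patient goes home is known only after randomisation, and effective treatment is one of the conditions for it. A patient still too symptomatic to leave has done badly on this endpoint, yet the rule removes that patient. If more such patients, or slower ones, are removed from one arm, that arm looks faster than it was. Equal numbers alone do not protect the comparison: if one arm loses its slowest patients and the other loses patients admitted for unrelated reasons, a difference appears with no true effect.

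At stake is a multiplicity-controlled claim of faster readiness. Read as a statement about all randomised patients, it would need support that the visible text does not plan. The visible text also has no table of admitted and overnight patients by arm. The non-missing N that SAP 9 reports combines them with the wrong-disease cases.

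**Working it through.** The plan gives no effect size, SD, power or admission rate for this endpoint, so there is no figure of its own to reproduce. The only usable input is the arm size: SAP 9.11 refers to "sample size justifications results in the need for 127 subjects per treatment arm", a number set for the primary. It cannot be checked, because its SD and alpha are redacted. Everything below is illustration. A rank-sum test is assumed because SAP 11.2 is not visible. With two key secondaries, the first Holm step is 0.05/2 = 0.025.

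**1. Tipping point (uses only the counts).** Let mC and mD be the excluded patients on cetirizine and diphenhydramine, n1 = 127 − mC and n2 = 127 − mD. P is the probability that a cetirizine patient is ready sooner than a diphenhydramine patient.

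- Discharged only: P = 0.5 + z·√[(n1+n2+1)/(12·n1·n2)].
- All randomised, excluded patients tied at the worst rank: P* = (n1·n2·P + n1·mD + 0.5·mC·mD)/127², tested with tie-corrected variance.

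Worked case, p = 0.025 (z = 2.241) with 4 v 3 excluded, so n1 = 123 and n2 = 124:

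- P = 0.5 + 2.241·√[248/(12·123·124)] = 0.5825.
- P* = (15,252·0.5825 + 123·3 + 0.5·4·3)/16,129 = 0.5741.
- Standard error 0.0363, so z = 0.0741/0.0363 = 2.04 and p = 0.041.

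| Discharged-only p | Excluded, cetirizine v diphenhydramine | All-randomised p |
|---|---|---|
| 0.025 | 3 v 3 | 0.031 |
| 0.025 | 4 v 3 | 0.041 |
| 0.025 | 8 v 3 | 0.12 |
| 0.025 | 3 v 8 | 0.008 |
| 0.01 | 5 v 3 | 0.025 (just above the threshold) |
| 0.001 | 11 v 3 | first count above 0.025 |

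Each extra cetirizine patient counted as not ready moves z by about 0.12. The 3 v 3 row shows that a result exactly at the threshold crosses it even with equal counts. A clear result (p = 0.001) needs a large imbalance.

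**2. Simulation (all parameters assumed).** There are 127 per arm and 16,000 trials per scenario. Readiness is 1 h plus a lognormal time (median 1 h, log-SD 0.6). Half of those ready before 2 h are held to exactly 2 h, to reflect the Protocol 4 rule "If symptom score is not zero prior to 2 hr, patient must be kept at the treatment center for at least 2 hours". With no true difference, the chance of declaring cetirizine faster at the 2.5% step is nominally 1.25%.

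| Excluded, cetirizine v diphenhydramine | Discharged only | Worst rank | False gain, min |
|---|---|---|---|
| 4% v 4%, unrelated | 1.2% | 1.2% | – |
| 3% v 2%, slowest | 2.6% | 1.3% | 1.3 |
| 6% v 2%, from slowest quarter | 4.1% | 0.6% | 2.5 |
| 6% v 2%, slowest | 5.8% | 0.8% | 4.3 |
| 4% slowest v 4% unrelated | 5.2% | 3.9% | 5.8 |

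Removing the slowest patients equally gives 1.3% at 1% v 1% and 1.75% at 2% v 2%, close to nominal. Reversing the types in the last row gives 5.8 min the other way. If 6% v 2% are all unrelated, discharged-only behaves correctly (1.1%), and worst rank wrongly calls cetirizine slower in 4.4% of trials.

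A second model (lognormal stay, median 2 h, CV 0.5, longest stays excluded, t-test) agrees in kind. Two-sided error at nominal 5% is 5.0% at 2% v 2% and 11.1% at 5% v 2%, against 5.2% and 5.1% for worst rank.

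**The case against.** **The decisive sections cannot be read.** SAP 11.2 is in the contents list but not in the supplied text, and the derivations in SAP 9.9 are redacted. The phrase in SAP 2 could also mean descriptive summaries only. A reader might infer that the plan has no all-randomised analysis and no count by arm; the documents do not support that. What stands is narrower: SAP 9.11 makes the value missing, so a test would drop these patients too unless one of those sections says otherwise.

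**Sedation is a weak route to exclusion.** A reader might infer that the sedation criterion pushes sedated patients out of the analysis. Note i of Protocol 4 limits the stay of a fit but sedated patient to 5 hours and has transport arranged. The plausible link runs mainly through lack of effective treatment or fitness for discharge.

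**Some stays have other causes.** Hospitals are enrolment settings, Protocol 2 describes drug-induced urticaria in hospital, and SAP 5 mentions onset while in the ED for another disease. Leaving out such patients need not bias anything.

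**The counts can be partly reconstructed.** SAP 10.2 lists per-protocol exclusions by arm with descriptions, so wrong-disease cases classed as major violations could be subtracted. SAP 12.2 summarises SAEs by arm. This helps but is incomplete: the SAE criteria in Protocol 8.2 name inpatient hospitalisation, not overnight observation, and Protocol 8.1 may keep disease-related events out of AE reporting.

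**The direction is unknown.** Most scenarios above load cetirizine. The pilot findings in Protocol 2 (similar efficacy, earlier discharge, less sedation) give no reason to expect that. Nor can the opposite be assumed. With a true 12-minute gain and 2% v 6% slowest excluded, the planned rule is conservative: power 43%, against 60% for worst rank.

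**The rule is prespecified and disclosed.** That prevents a choice driven by the data, but it does not remove selection.

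**Conclusion.** The point holds in limited form. On the visible text, the comparison of time to readiness is likely to be restricted to patients who went home, and its result can be biased either way if exclusions differ by arm in number or type. The size cannot be stated without admission rates. It is negligible if exclusions are few and alike, but enough to move a borderline p-value across 0.025 if one arm has a few more.

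The documents do not support a claim that the rule favours cetirizine, nor that the primary is compromised: the primary uses the pruritus score and its own handling rules. Neither analysis is right in general, because discharged-only fails when exclusion reflects poor response and worst rank fails when it does not. Severity is minor. The figures rest on 127 per arm, an assumed rank-sum test and, for the simulation, assumed distributions and rates.

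**What to change.** Before unblinding, and unless SAP 11.2 or 9.9 already does so:

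1. Keep the planned analysis as it is.
2. Report admitted and overnight patients by arm, separately from wrong-disease cases. Give the reason where it is recorded (urticaria or treatment-related, or unrelated), classified blind.
3. Add one sensitivity analysis of all randomised patients in which admitted and overnight patients rank as not ready for discharge, with a Wilcoxon-type test. No readiness time is needed for them. Read it together with the reasons.
4. If the two analyses disagree, describe a faster-readiness result as applying to patients who went home.

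The cost is one analysis and a few table rows, with no new patients or procedures; the reason for admission may not be on the CRF. In the simulation with a true 12-minute gain, tested at the 2.5% step, worst rank lowers power from 57% to 53% at 2% v 2% and from 57% to 51% at 4% v 4%. If 6% v 2% are excluded for unrelated reasons it falls from 57% to 30%, which is why this should be a sensitivity analysis and not a replacement. A log-rank version costs more (56% with no exclusions, 41% at 2% v 2%, 33% at 4% v 4%).

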**3. STUDY DESIGN**

This is a multi-center, parallel group, randomized, double-blind, active controlled, phase III clinical trial of cetirizine injection 10 mg/mL versus diphenhydramine injection 50 mg/mL (Benadryl or generic equivalent) in approximately 254 subjects who either present to Emergency Departments, hospitals, allergy clinics or Urgent Care Centers with acute urticaria, or developed acute urticaria following allergen challenge at an Allergy Clinic.

Subjects, or their guardians, will sign an informed consent and will be evaluated for eligibility for inclusion to treat. Eligible subjects will be assessed for baseline characteristics, medical and surgical histories, concomitant medications and given a brief physical exam. Then subjects will be randomized, in a 1:1 ratio, to blindly receive either cetirizine 10 mg/mL injection or diphenhydramine 50 mg/mL injection. At randomization, the subjects will be given a Subject ID Number that corresponds to the randomization schedule and administered study medication based on the kit contents. Neither the subjects, nor study personnel will know which study drug is given.

Efficacy assessments will include patient rated severity of pruritus, and physician assessments of Extent Urticaria/Erythema, etc. Subjects will remain in the treatment center for at least after the 1 hr assessment, after which they may be discharged at the physician's discretion.

Safety will be monitored through the reporting of adverse events for up to 28 days following treatments and by monitoring vital signs at planned intervals from admission into the treating facility until readiness for discharge. After 24 and 48 hours after discharge, subjects will be contacted by phone for follow up questions regarding recurrence of symptoms, new symptoms, additional medication taken, side effects from medication taken after discharge, relapse requiring a return to treatment center and return to normal activities. The schedule of assessments is outlined in [Table 1](#).

